1.1 Background

Heart transplantation is a lifesaving procedure for some children. However, the long-term success of a heart transplant is often limited by inflammatory processes leading to progressive narrowing of blood vessels that supply oxygen to the heart, known as Coronary Allograft Vasculopathy (CAV).

CAV is a leading cause of death beyond 3 years after heart transplant and remains an important limitation to long term survival and graft longevity [1]. Once established, CAV is refractory to conventional medical or surgical approaches, and constitutes the most important predictor for all-cause mortality in this patient population. Data from 2017 derived from angiography reports found that 67% of patients (of all ages) were free from CAV 10 years after their transplant [2]. However, early onset of disease or the true burden of disease may be well underestimated as coronary angiography is not the most sensitive modality of diagnosis. Once a diagnosis of CAV has been confimed, graft survival is also significantly reduced across all age groups, with infants being the worst affected (with a median survival of 2 years after diagnosis) [2].

CAV can occur despite the use of immunosuppressive drugs that are also linked to morbidity and mortality themselves, with side effects including increased risk of infection, reactivation of viruses and Post-Transplant Lymphoproliferative Disorder (PTLD).

No effective treatments are available for established CAV. Revascularization has not shown to improve outcome and re-transplantation is limited by donor availability. Re-transplantation is rarely possible due to donor shortages and the presence of alloantibodies induced by the previous transplant.

Recent data from a multicentre study, involving GOSH, showed that impaired graft function associated with CAV was a poor prognostic sign [3]. Interestingly, the incidence of CAV in children has not declined over time. Therefore, the prevention of CAV, the main cause of graft damage, is still an unmet goal. The urgency is reflected by the clear directive from the Family Steering Group at Great Ormond Street Hospital.

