3.2 Objectives and endpoints

Objectives	Outcome Measures/Endpoints
Primary Objective: To determine safety and optimal tolerated dose of TR006 to prevent CAV in paediatric heart	Primary Endpoint: Occurrence and nature of Dose-Limiting Toxicities (DLTs) occurring within 4 weeks post-
transplant patients in a phase I study.	infusion of the expanded autologous thymus derived Treg product (ATIMP).
Secondary Objectives:	Secondary Endpoints:
1. To assess the feasibility of generating TR006 in the Good Manufacturing Practice facility.	Amount of TR006 manufactured per patient.
2. To investigate the clinical and immunological	Assessment of Immunological response:
responses to TR006 in paediatric heart	• Frequency of circulating leukocyte subsets.
transplant patients.	• Quantity of alloantigen-specific conventional T cells, Tregs and CD8+.
	 Presence of anti-HLA to evaluate tissue infiltrating cells.
	Assessment of clinical response:
	• Diagnosis of CAV as measured by coronary angiography within 24 months post-infusion of TR006.
	 Graft loss as measured by inclusion of patient on the re-transplant waiting list through rejection (acute or chronic) within
	24 months post-infusion of TR006.
	• Recipient mortality within 24 months post- infusion of TR006.
	 Acute graft rejection as measured by endomyocardial biopsy (EMB) within 24 months post-infusion of TR006.
	• Antibody-mediated rejection as measured by development of donor specific antibodies within 24 months post-infusion of TR006.

r	
	 Infection related rehospitalisation events within 24 months post-infusion of TR006.
	 (Cardiac function) Left ventricular ejection fraction as measured by echocardiography monthly for 12 months and at 24 months post-infusion of TR006.
	 (Renal function) Mean calculated GFR at 24months post-infusion of TR006.
	• Description of non-DLT adverse events and those occurring beyond week 4 and up to 24 months post-infusion of TR006.
	 Immunosuppressive doses at 12 and 24 months post-infusion of TR006.
3. To assess the feasibility of retaining participants for the duration of the study and completion of study visits and assessments	Number of study visits completed per participant.
	 Responses to items in questionnaires or surveys exploring the study and treatment experience of the participants and their parents/guardians.

4 Assessment and Management of Risk

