- Height and weight. (All visits)
- ECG (12-Lead). (All visits)
- Echocardiography. (All visits)
- Intravascular ultrasound (only for children over 25kg). (Transplant Follow-up Month 3)
- Coronary angiography (only for children over 25kg). (Transplant Follow-up Month 3)
- Clinical blood tests (Full blood count, liver profile, renal profile, LDH, EBV, CMV viral load, full blood borne infectious diseases* and HLA antibody testing (includes panel reactive antibodies and donor specific antibodies)⁺). (All visits)
- Urine pregnancy test (if applicable). (Transplant Follow-up Month 3)
- Translational research blood samples. (Transplant Follow-up Day 14 and Transplant Followup Month 3)
- Clinical cardiac biopsy. (Transplant Follow-up Day 14 and Transplant Follow-up Month 3)
- * Full blood borne infectious diseases testing on Transplant Follow-up Month 3 only.

⁺ HLA antibody testing (includes panel reactive antibodies and donor specific antibodies) on Transplant Follow-up Day 14 and Transplant Follow-up Month 3.

Baseline (Day 0) can occur as soon as the results from the clinical cardiac biopsy (obtained at the Transplant Follow-up 3 Months study visit) have been reviewed by the Study Team. Biopsy results normally take 2-3 days to be reported.

If 30 days elapse after the Transplant Follow-up Month 3 study visit, then Transplant Follow-up Month 4 should be carried out. Similarly, if 30 days elapse after the Transplant Follow-up Month 4 study visit, then Transplant Follow-up Month 5 should be carried out.

If TR006 dosing is able to occur within 30 days after the Transplant Follow-up Month 3 study visit, then neither the Transplant Follow-up Month 4 or the Transplant Follow-up Month 5 study visits need to be carried out and the participant can proceed straight to Baseline (Day 0).

However, if the participant requires the Transplant Follow-up Month 4 study visit and then is able to receive the TR006 dose within 30 days after this visit, then the Transplant Follow-up Month 5 study visit does not need to be carried out and the participant can proceed straight to Baseline (Day 0).

Additional transplant follow-up (if required): Transplant Follow-up Month 4 and Transplant Follow-up Month 5.

- Inclusion/Exclusion criteria review. (All visits)
- Medical History. (All visits)
- Concomitant Medication collection. (All visits)
- Adverse Events collection. (All visits)
- Doctor review (including physical examination). (All visits)
- Vital signs. (All visits)

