- Doctor review (including physical examination).
- Vital signs.
- Height and weight.
- ECG (12-Lead).
- Echocardiography.
- Intravascular ultrasound (only for children over 25kg).
- Coronary angiography (only for children over 25kg).
- Clinical blood tests (Full blood count, liver profile, renal profile, LDH, EBV, CMV viral load and HLA antibody testing (includes panel reactive antibodies and donor specific antibodies)).
- Urine pregnancy test (if applicable).
- Translational research blood samples.

Safety Follow-up: Month 12 post TR006 infusion. (+/- 4 weeks)

- Concomitant medication collection.
- Adverse Events collection.
- Doctor review (including physical examination).
- Vital signs.

- Height and weight.
- ECG (12-Lead).
- Echocardiography.
- Clinical blood tests (Full blood count, liver profile, renal profile, LDH, EBV and CMV viral load).
- Translational research blood samples.

End of Study: Month 24 post TR006 infusion. (+/- 4 weeks)

- Concomitant medication collection.
- Adverse Events collection.
- Doctor review (including physical examination).
- Vital signs.
- Height and weight.
- ECG (12-Lead).
- Echocardiography.
- Clinical blood tests (Full blood count, liver profile, renal profile, LDH, EBV, CMV viral load and HLA antibody testing (includes panel reactive antibodies and donor specific antibodies)).
- Urine pregnancy test (if applicable).
- Translational research blood samples.

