Respiratory rate (rpm)	30-40	25-35	25-30	20-25	14-18			
Blood pressure Systolic mmHg	80-90	85-95	85-100	90-100	100-140			
Temperature (°C)	35-37	35-37	35-37	35-37	36-37.5			
Saturations (%)	94-98							

ECG:

Performed by an appropriate trained and delegated clinician to measure:

- Ventricular rate.
- Rhythm.
- QRS axis.
- QRS duration.
- Corrected QTC interval.

Comparison with previous ECG in medical records to occur where appropriate.

Transthoracic Echocardiogram:

Performed by an appropriate trained and delegated clinician to measure:

- Standard Transthoracic Echocardiogram views for cardiac structures and anastomoses sites from apical, parasternal long axis, parasternal short axis and suprasternal windows.
- Systolic functional assessment: Left Ventricular Ejection Fraction (LVEF) calculated by Simpson's biplane and on m-mode (Ejection Fraction by Teichholz formula).
- Right Ventricular function- comment on visual assessment and measurement of Tricuspid Annular Plane Systolic Excursion (TAPSE).
- Diastolic function parameters using tissue doppler interrogation: Mitral E wave and A wave velocities and ratio. Septal and lateral E/E' ratios and TVS' wave velocity.
- Any significant valvopathy on 2D echo and colour interrogation with doppler measurements (as required).
- The presence of pericardial effusion.
- Interval change(s) from previous tests.

Coronary vessel imaging:

The following imaging procedures are to be performed only in children above 25kg by an appropriate trained and delegated clinician:

- Coronary angiogram.
- Intravascular Ultrasound.

Blood tests:

The following tests are to be performed by an appropriate trained and delegated clinician:

- Clinical blood tests to assess: Haematology (full blood count), liver profile (albumin, alkaline phosphatase, total bilirubin and ALT levels), renal profile (sodium, potassium, creatinine and urea levels), LDH levels, EBV and CMV.
- Additional clinical blood tests to assess: bone profile, creatinine kinase (CK), CRP, ferritin, magnesium, uric acid levels and to coagulation screen.
- HLA antibody testing (includes panel reactive antibodies and donor specific antibodies)'
- Blood borne infection screen (with further details in Table 2 for the specific diseases and markers assessed).

Additional research blood tests will be collected at various study visits (as per Table 8) but will not be used for the safety assessment purposes.

Endomyocardial cardiac tissue biopsy:

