10.1 Statistical methods to be employed (plan of analysis)

Biometric evaluation will be performed under the responsibility of [name]. Demographic data and baseline characteristics will be summarized to describe the populations analysed in this study (both all participants and participants administered each dose level). Efficacy parameters: clinical and immunological responses will be reported descriptively based on the per-protocol population. Time to first response will be summarized by Kaplan-Meier curve. Median time to event estimation as well as the associated 95% CI will be reported. All other secondary endpoints will be summarized by rates and corresponding 95% CIs.

All safety data will be analysed descriptively. Safety data will be reviewed between each patient cohort, with interim analyses provided to the DMC in order for decisions related to the next patient cohort to be made (decisions will be based on the 3+3 dose escalation design described in trial design section).

Statistical comparisons between patient populations are unlikely to be utilised, but if needed a 5% level of significance will be used.

A Statistical Analysis Plan will be written and will be signed off prior to database lock and will provide detailed information on all statistical analyses planned for the study.

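### The angiographic CAV endpoint runs to 24 months in all analysed children, but the only scheduled post-infusion angiogram is at Month 9 and only in children over 25 kg; the paired ultrasound feeds no endpoint

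*Protocol*

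**What the plan says.** Section 3.2 has one CAV endpoint: "Diagnosis of CAV as measured by coronary angiography within 24 months post-infusion of TR006". The synopsis refers only to the development of CAV.

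Coronary imaging is scheduled twice. Before infusion, section 7.3 lists "Intravascular ultrasound (only for children over 25kg). (Transplant Follow-up Month 3") and an angiogram at the same visit with the same weight limit. After infusion, section 7.5 lists "Intravascular ultrasound (only for children over 25kg") and "Coronary angiography (only for children over 25kg") at Month 9 only. Neither test is listed at Month 12 or Month 24, and Tables 3, 5 and 16 in Appendix B agree. Section 9.7 repeats the limit: "The following imaging procedures are to be performed only in children above 25kg". Eligibility (section 6.1) starts at 0.5 years and sets no minimum weight.

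On analysis, section 10.1 says that "clinical and immunological responses will be reported descriptively based on the per-protocol population", and that the remaining secondary endpoints are summarised as rates with 95% confidence intervals. Section 10.5 takes in every eligible recruited participant. Neither section mentions whether a child was imaged.

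On the test itself, section 1.1 says that "coronary angiography is not the most sensitive modality of diagnosis". Ultrasound appears in the visit lists, the schedules and the section 9.7 safety procedures, but in no endpoint and in no analysis in section 10.

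**The concern.** The endpoint promises more than the schedule can deliver. It covers 24 months and, through sections 10.1 and 10.5, populations defined without regard to imaging. The scheduled measurement covers 9 months and the larger children only.

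CAV is the condition TR006 is meant to prevent, so its rate will be read closely even in a Phase I trial, and a Phase II trial is foreseen in section 2.1. With so few children, zero angiographic cases is a likely result whether or not the product works. What a zero means then depends on who was looked at and until when. If the report shows 0/9 at 24 months when some of the nine had no angiogram and none had a scheduled one after Month 9, it looks firmer than the data allow.

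The protocol also collects a before-and-after ultrasound pair in the same children and assigns it to no endpoint. It would give something to describe per child when the angiographic count is zero.

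**Working it through.** **The plan's own figure.** The protocol gives no size or precision calculation for CAV. Its only sample size figure is 9 to 12 (section 10.2), which follows from the dose rules in section 5.1: 3 low + 3 high + 3 high = 9; 6 low + 3 high = 9; and 6 low + 3 high + 3 more after one DLT in three at the high dose = 12. Early safety stops end sooner.

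**Window.** The last scheduled angiogram is at Month 9 of 24. Uncovered share: (24 − 9)/24 = 15/24 = 62.5%.

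**Denominator.** With no cases among k children, the two-sided 95% Clopper-Pearson upper limit is 1 − 0.025^(1/k). The number of children over 25 kg is not in the protocol, so k is varied.

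| Children in denominator | Upper limit for 0/k |
|---|---|
| 9 | 33.6% |
| 6 | 45.9% |
| 4 | 60.2% |
| 3 | 70.8% |

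A single case reads 1/9 = 11% with nine in the denominator, but 1/3 = 33% if three were imaged.

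**How likely is zero?** Section 1.1 reports from angiography that "67% of patients (of all ages) were free from CAV 10 years after their transplant". Assume a constant hazard, so the probability of CAV over t years is 1 − 0.67^(t/10). Infusion is 3 to 6 months after transplant, so the two scheduled angiograms are 9 to 12 months apart (visit windows ignored):

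- t = 0.75: 1 − 0.67^0.075 = 3.0% per child
- t = 1.00: 1 − 0.67^0.100 = 3.9% per child

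The probability of no new case among k imaged children, with no treatment effect, is 0.67^(kt/10):

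| k imaged | t = 0.75 | t = 1.00 |
|---|---|---|
| 3 | 91% | 89% |
| 6 | 84% | 79% |
| 9 | 76% | 70% |

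For k = 9, half the hazard gives 84% to 87% and double the hazard gives 49% to 58%.

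**Risk after the last scheduled angiogram.** On the same hazard, the risk from infusion to Month 9 is 3.0%. For a child CAV-free at Month 9, the risk from Month 9 to Month 24 (t = 1.25) is 1 − 0.67^0.125 = 4.9%. More of the expected risk therefore falls in the part of the window without a scheduled angiogram.

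**What ultrasound could add.** For a mean within-child change, the 95% half-width in SD units is t(0.975, n − 1)/√n: 0.77 at n = 9, 1.05 at n = 6, 1.59 at n = 4 and 2.48 at n = 3. This supports a per-child listing and little more.

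**The case against.** The strongest reply is that nothing in the protocol scores an unimaged child as free of CAV. A reader might infer that it does, because sections 10.1 and 10.5 are broader than the imaged group. The text does not support that reading. The endpoint is defined by angiography, so a child without an angiogram has no measurement, and section 10.5 says who enters the analysis, not how an unobserved outcome is handled. Missing-outcome rules commonly belong to the SAP. This stands, so the denominator comparison holds only if unimaged children are in fact counted.

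Second, 24 months can be read as an outer limit for a diagnosis. A clinically indicated angiogram after Month 9, or in a smaller child, would properly count. This also stands. A rate to 24 months nevertheless has no scheduled examination behind it after Month 9, and a SAP cannot supply one.

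Third, restricting the rate to children imaged at both visits would do harm. It could drop a child who dies or loses the graft before Month 9, one who passes 25 kg between visits, or a small child with confirmed CAV. This is correct, and the fix avoids that restriction.

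Fourth, leaving ultrasound out of the endpoints contradicts nothing. It has a safety use in section 9.7, section 1.1 does not name it as the more sensitive test, and without a control group a change cannot be attributed to TR006. All of this is true, and it limits the proposal to a descriptive listing.

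**Conclusion.** The point holds as a mismatch between the endpoint and the schedule. Section 3.2 sets a 24-month angiographic endpoint; the design schedules one post-infusion angiogram, at Month 9, in children over 25 kg. That leaves 62.5% of the window and all smaller children without a scheduled measurement.

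The possible overstatement (34% against 46% or 71%) is conditional on unimaged children entering the denominator and on an assumed 6 or 3 imaged out of 9. The probability of a zero count rests on a constant hazard from one all-ages figure, which section 1.1 itself warns may understate early disease; at double the hazard with nine imaged, zero is about an even chance. The mismatch depends on neither assumption.

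The gain from ultrasound cannot be quantified from the protocol. This is a descriptive secondary endpoint in a Phase I trial, and the primary endpoint and dose decisions are unaffected. It is a minor point that is cheap to correct.

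**What to change.** Amend section 3.2 as follows.

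1. Report the CAV rate from scheduled imaging at Month 9 among children with a post-infusion coronary angiogram. State that denominator and the 25 kg limit beside it. Do not count unimaged children as CAV-free, and do not require imaging at both visits.
2. Report every CAV diagnosis up to 24 months as cases alongside that rate, including those from unscheduled angiograms or in smaller children. List deaths and graft losses before Month 9 with them, so that no case drops out.
3. Add a descriptive exploratory listing, per child and by dose received, of the change on intravascular ultrasound from Transplant Follow-up Month 3 to Safety Follow-up Month 9 where both exist, with the measure chosen by the sponsor. Make no claim that the change is due to TR006.

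The cost is endpoint wording, one denominator statement and two listings, with no new procedure or visit. The downside is a smaller stated denominator, and an imprecise, uncontrolled ultrasound description confined to the larger children.

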- 2. The TR001 phase I/II study based at Oxford and King's College London (NCT02129881) comprised 15 patients who were enrolled into the trial; 2 patients were withdrawn due to failure to expand sufficient Tregs (n=2) and one due to bacterial contamination of the Treg product. Out of 12 remaining patients, there were no Serious Adverse Reactions (SARs) or episodes of graft rejection, and a lower incidence of opportunistic infections compared to the reference group. Participants received cell therapy alongside standard of care immunosuppression. Infused cell doses are shown in Table 1. In a new currently ongoing trial, TR001 is being administered to living-donor kidney transplant recipients as part of a single centre phase II trial The TWO Study. The overall aim of this study is to evaluate the efficacy of Tregs in renal transplantation [9].

Results of the King's College London and Oxford study were pooled and published as with the ONE study, with a detailed paper of the Treg trial to follow [10]. Analysis of the adverse event data showed no safety issues when compared to the reference group trial. Infection rates were lower in the trials of cell-based medicinal products but the rejection rate was found to be similar across all trials.

Another phase I study (NCT02088931) from University of California treated 3 renal transplant recipients with an absolute Treg cell dose each of 319, 321 and 364x10⁶ (equivalent to 4.5x10⁶/kg, 4.6x10⁶/kg and 5.2x10⁶/kg assuming a body weight of 70kg). There were no opportunistic infections or SAEs, no CMV or polyoma neuropathy, no rejection, or cases of donor specific antibodies at one-month post infusion [26].

Autoimmune disorders

Clinical trials using autologous expanded Tregs have been conducted in specific autoimmune disorders, namely type I diabetes, and systemic lupus erythematosus, summarised in **Table 1** below).

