If both doses are tolerated, there will be a total of n=9 patients in the study (3 at the low dose and 6 at the high dose or 6 at the low dose and 3 at the high dose). If the higher dose can only be assessed from Cohort 3 and there is 1/3 DLT observed, a further 3 patients will need to be treated at this dose to establish the highest tolerated dose. In this scenario, funding for a further 3 participants will be applied for and the total sample size will be 12 participants.

A DLT will be determined from data collected during the 4-week period post TR006 infusion. Patients with no undue toxicity will be managed and continued on therapy. A DLT will be graded according to the National Cancer Institute's Common Terminology Criteria for Adverse Events (CTCAE) on a 1 to 5 sale as follows [37]:

Grade 1: Mild adverse event Grade 2: Moderate adverse event Grade 3: Severe and undesirable adverse event Grade 4: Life-threatening or disabling adverse event Grade 5: Death.

A DLT is a toxicity considered to be related to TR006. The following events will be considered DLTs:

Occurring in the first 72 hours post infusion:

- CTCAE ≥ grade 2 cytokine release syndrome
- CTCAE ≥ grade 2 injection site reaction
- CTCAE ≥ grade 2 fever and/or rigors
- CTCAE ≥ grade 3 bronchospasm
- CTCAE \geq grade 3 hypoxia

Occurring in the first 4 weeks post TR006 infusion:

• CTCAE \geq grade 3 infection

• Moderate or severe acute rejection (as defined by the International Society for Heart and Lung Transplantation (ISHLT) criteria grade II-III) [38]

- CTCAE \geq grade 3 haematological complication (neutropenia, thrombocytopenia, anaemia).
- Any CTCAE ≥ grade 3 toxicity not clearly related to underlying disease

6 Population

9 paediatric patients on the heart transplant register at GOSH will be recruited to the study.

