6.2 Exclusion Criteria

- Active viral infection (with HIV (positive for HIV antibody type 1 or 2), hepatitis B (positive HBSAg), hepatitis C (anti-HCV antibody detection), Human T lymphotropic virus (HTLV antibody I/II detection) and syphilis (Treponema pallidum antibody detection)) at date of admission for transplant (Please refer to Table 2 for more details).
- 2. Age under 0.5 year or over 16 years at date of consent and at date of transplant.
- 3. Multi-organ transplant.
- 4. Highly-sensitised patients at high risk of rejection assessed by HLA antibody measurement (cumulative risk of Mean Fluorescent Intensity (MFI) being >5000 of donor specific antibodies from HLA antibody testing).
- 5. Allergy to any component / excipients used for the manufacture of TR006.
- 6. Previous recipient of any organ transplant.
- 7. History of previous sternotomy surgical procedure for congenital heart defect during which has had previous partial or full thymectomy.
- 8. Confirmed diagnosis of DiGeorge Syndrome with absent thymus.
- 9. Participation in another interventional Clinical Trial of Investigational Medicinal Product during the study or within 28 days prior to date of transplant (at the Chief Investigator's discretion).
- 10. Pregnant and lactating patients (females of childbearing potential* with a positive urine pregnancy test at date of transplant).
- 11. Female patients of childbearing potential* who are not willing to use a highly effective method of contraception** for the duration of the trial (defined as from date of transplant to 12 months

post Treg infusion) to prevent pregnancy, or abstain from heterosexual activity.

*Females of child-bearing potential are females who have experienced menarche and are not surgically sterilised (e.g., hysterectomy, bilateral salpingectomy or bilateral oophorectomy) or post-menopausal. Postmenopausal state is defined as no menses for 12 months without an alternative medical cause. A high follicle stimulating hormone (FSH) level in the postmenopausal range may be used to confirm a postmenopausal state in women not using hormonal contraception or hormonal replacement therapy (HRT). However, in the absence of 12 months of amenorrhea, confirmation with more than one FSH measurement is required.

****** Highly effective methods of contraception are those with a failure rate of < 1% per year when employed consistently and correctly. For example:

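### The secondary endpoint called antibody-mediated rejection is measured by donor-specific antibody alone, so its reported rate would be a rate of new antibody, not of rejection

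*Protocol*

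**What the plan says.** Section 3.2 sets out the secondary endpoints under the second secondary objective. Under the sub-heading "Assessment of clinical response" there are two separate rejection items that differ in how they are measured:

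- The first item rests on tissue: "Acute graft rejection as measured by endomyocardial biopsy (EMB) within 24 months post-infusion of TR006".
- The second item rests on a blood test: "Antibody-mediated rejection as measured by development of donor specific antibodies within 24 months post-infusion of TR006".

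The second item gives no graft criterion, and no other section defines antibody-mediated rejection or adds one. The synopsis mentions acute and chronic rejection only.

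Other sections use donor-specific antibody and rejection as distinct concepts:

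- Section 6.2, exclusion 4, concerns "Highly-sensitised patients at high risk of rejection assessed by HLA antibody measurement", with the cut-off given as "cumulative risk of Mean Fluorescent Intensity (MFI) being >5000 of donor specific antibodies from HLA antibody testing".
- Section 1.4, describing a phase I kidney transplant study, reports "no rejection, or cases of donor specific antibodies at one-month post infusion".
- Section 5.1, in the list of dose-limiting toxicities, has "Moderate or severe acute rejection (as defined by the International Society for Heart and Lung Transplantation (ISHLT) criteria grade II-III".

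Section 10.1 says that secondary endpoints of this kind will be summarised as rates with 95% confidence intervals.

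**The concern.** Donor-specific antibody is found in blood; rejection is something that happens to the graft. Section 3.2 names the second and measures only the first. A child whose HLA test turns positive while the graft stays normal meets the endpoint and is reported as having had antibody-mediated rejection.

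What is at stake is how a small paediatric report is read. With nine treated children, each case is a visible share of the total. Section 2.1 says the results are meant to lead to a Phase II trial. A rejection figure that is really an antibody figure could be carried forward, or compared with other programmes, under the wrong name.

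**Working it through.** **Does any section add a graft criterion?** The protocol states no figure for this endpoint, so there is nothing to reproduce. The check is to set the relevant sections side by side.

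| Section | Role of donor-specific antibody | How rejection is established |
|---|---|---|
| 3.2, acute rejection item | none | endomyocardial biopsy |
| 3.2, antibody-mediated rejection item | the whole measure | antibody only |
| 6.2, exclusion 4 | marker of rejection risk, with an MFI cut-off | not applicable |
| 1.4, kidney study | outcome listed beside rejection | separate outcome |
| 5.1, dose-limiting toxicities | none | ISHLT grade |

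The antibody-mediated item is the only one that equates the two.

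**When are blood and tissue examined after infusion?** From section 7.5 and Table 5:

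- HLA antibody tests: Months 3, 9 and 24.
- Scheduled cardiac biopsy: Month 3 only.

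Antibody first found at Month 9 or Month 24 therefore has no scheduled tissue result beside it, yet would be counted as rejection.

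**How far does one antibody-only child move the result?** Inputs: n = 9, or 12 if expanded (section 5.1), and a rate with a 95% interval (section 10.1). Two assumptions are added: every treated child is in the denominator, and the interval is exact (Clopper-Pearson).

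For x = 0 the upper limit is 1 − 0.025^(1/n):

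- n = 9: 1 − 0.025^(1/9) = 0.336
- n = 12: 1 − 0.025^(1/12) = 0.265

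For x = 1 the lower limit is 1 − 0.975^(1/n), which gives 0.003 for n = 9 and 0.002 for n = 12. The upper limit is the 0.975 quantile of a beta distribution with parameters 2 and n − 1, which gives 0.482 and 0.385.

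| n | no antibody-only child | one antibody-only child |
|---|---|---|
| 9 | 0/9 = 0% (0 to 33.6%) | 1/9 = 11.1% (0.3 to 48.2%) |
| 12 | 0/12 = 0% (0 to 26.5%) | 1/12 = 8.3% (0.2 to 38.5%) |

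**How likely is at least one such child?** The documents give no rate q of antibody without graft involvement, so q is assumed over a range. The chance is 1 − (1 − q)^n; for example, with q = 0.10 and n = 9, 1 − 0.9^9 = 0.613.

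| assumed q | n = 9 | n = 12 |
|---|---|---|
| 5% | 37% | 46% |
| 10% | 61% | 72% |
| 20% | 87% | 93% |
| 30% | 96% | 99% |

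These chances illustrate the range and are not estimates for this trial.

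**The case against.** The best defence is that the measure stands in the endpoint's own sentence, so a careful reader can see that it rests on antibody. The endpoint is one of many descriptive secondary ones, and a statistical analysis plan, which section 10.1 promises, could add a baseline and a threshold. This limits the harm but does not remove the fault. The protocol does not leave the measure open: it fixes it as antibody and names it rejection, and an analysis plan that follows the protocol inherits the name.

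The defence does succeed against three stronger readings that a reader might infer.

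- *Antibody present before infusion will be counted.* The endpoint speaks of development, which ordinarily means new onset. Section 7.3 schedules HLA tests before infusion at enrolment, Day of Transplant, and Day 14 and Month 3 after transplant, with further tests at Months 4 and 5 if those visits are held. What is unstated is only which of these is the reference.
- *One test result is counted twice.* The immunological list has "Presence of anti-HLA to evaluate tissue infiltrating cells". Its wording is unclear, since section 7.7 studies infiltrating cells on biopsy tissue. Anti-HLA antibody is also broader than donor-specific antibody, because the HLA test covers panel-reactive antibody too. No composite or score exists in which a result could enter twice.
- *Antibody-mediated rejection seen on biopsy without detected antibody would be lost.* The biopsy endpoint in section 3.2 is not limited to cellular rejection, so such a case can be reported there. It would lack the antibody-mediated label, but it would not disappear.

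One further caution stands. A definition based on biopsy alone would have no scheduled assessment between Month 3 and Month 24 post-infusion, and no section says that biopsies are read for antibody-mediated injury. Exchanging one rule for the other without saying so could turn over-counting into under-counting.

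**Conclusion.** The point holds as a wrong endpoint rule. What section 3.2 calls antibody-mediated rejection is new donor-specific antibody, and the protocol's own usage in sections 1.4, 5.1 and 6.2 treats the two as different. Each antibody-only child adds 1/9 (11 percentage points) to the reported rejection rate, or 1/12 (8 points) with twelve children, provided all treated children are in the denominator. Whether this will happen cannot be read from the documents, because they give no rate of antibody without graft involvement.

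A reader might also infer that the trial's safety decisions are compromised. The documents do not support that: rejection as a dose-limiting toxicity is graded by ISHLT criteria, and this endpoint enters neither the escalation and stopping rules nor the sample size. The correction is worth making before results are reported, but it is a matter of naming and reporting.

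**What to change.** In section 3.2:

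1. Rename the item *new (de novo) donor-specific antibody within 24 months post-infusion*, and do not report it as rejection.
2. Name the reference as the last HLA test before infusion: Transplant Follow-up Month 3, or Month 4 or 5 if that visit was held. HLA testing is not listed at Baseline Day 0, so the protocol should say this outright.
3. Use the label antibody-mediated rejection only for cases with supporting findings on a biopsy already taken, and state which findings count. Confirm that the biopsy reports record them, since the protocol does not say so.
4. State that no biopsy is scheduled after Month 3 post-infusion. Children first positive at Month 9 or 24 with no biopsy available are then reported as antibody-positive, graft status not assessed by biopsy.

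The renaming and the reference test cost only wording and use HLA tests already scheduled. The synopsis has no definition of antibody-mediated rejection to reword. Item 3 adds no biopsy, but it depends on what the existing biopsy reports contain.
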